#### **6.4.4 Safety Population**

All subjects who receive at least one application of study drug and have at least one post-Baseline safety assessment will be included in the Safety population and analyzed according to the treatment received. All safety analyses will be performed using the Safety population.

### **6.4.5 Per-Protocol Population**

All subjects in the ITT population who complete the Day 85 visit without noteworthy study protocol violations will be included in the PP population and analyzed according to the treatment group received. The PP population will include subjects in the ITT population who do not meet any of the following criteria:

- Violated the inclusion/exclusion criteria;
- Have taken any interfering concomitant medication;
- Has missing IGA assessment at the Day 85 visit;
- Have missed both the Day 29 and Day 57 visits;
- Have not been compliant with the dosing regimen (i.e. subjects must apply 80 – 120% of the expected applications of study medication during participation in the study);
- Out of visit window at the Day 85 visit by  $\pm 7$  days;

Subjects that discontinue from the study due to an AE related to study treatment or documented lack of treatment effect will be included in the PP population. Prior to breaking the blind, other additional criteria may be added to the list to accommodate for unforeseen events that occurred during the conduct of the trial that result in noteworthy study protocol violations.

All efficacy analyses will be performed on the PP population with results considered as supportive.

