#### **6.1.5 Handling of Dropouts or Missing Data**

All efforts will be made to minimize the occurrence of missing data. It is not expected that dropout rates will differ between groups. Therefore, the primary method of handling missing efficacy data in the ITT and mITT analysis set will be based on LOCF. Summary of efficacy variables for the PP subjects will be based on available data. No imputation will be done for non-efficacy related variables.

If a partial date is reported where the day is missing, then the day will be imputed as the first day of the month unless the month is the same month as the first application of study drug then the day will be that of first application with the month and year remaining the same. If a partial date is reported where the month is missing, then the month will be imputed to January unless the year is the same year as the first application of study drug then the month will be that of first application with the year remaining the same. If a partial date where both the day and month is missing, follow details as stated previously.

Missing AE start dates will be imputed using partial date imputation rules as previously described in this Section.

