### **6.1.9 Use of an Efficacy Subset of Subjects**

One subset of interest is the mITT population. This subset is defined in order to better assess the effects of treatment on target areas; see Section 6.4.3 for definition.

Subjects randomized to study drug who complete the Day 85 visit without noteworthy study protocol violations, including compliance with study drug application, and completion of efficacy evaluations on Day 85 will form the PP population. Any noteworthy protocol violations will be defined at the time of evaluability evaluation, the time between the database soft lock and hard lock before unblinding.

Both mITT and PP analyses will allow for a further exploration of overall efficacy of BTX 1204.

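### SAP 6.4.5 says that subjects who stop for a related AE or lack of effect stay in the PP population, but the other PP rules leave those who exit before Day 71 out of the Day 85 PP analysis

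*SAP*

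**What the plan says.** **Inclusion.** SAP 6.4.5 opens with "All subjects in the ITT population who complete the Day 85 visit without noteworthy study protocol violations will be included in the PP population". After its list of exclusions it adds that subjects who discontinue "due to an AE related to study treatment or documented lack of treatment effect will be included in the PP population".

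**Exclusion.** The list between those two sentences removes a subject for any of these reasons, among others:
- "Has missing IGA assessment at the Day 85 visit";
- "Have missed both the Day 29 and Day 57 visits";
- "Out of visit window at the Day 85 visit by" more than 7 days in either direction;
- compliance outside 80–120% of expected applications.

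SAP 6.1.9 gives a second definition. PP subjects are those "who complete the Day 85 visit without noteworthy study protocol violations", and "completion of efficacy evaluations on Day 85 will form the PP population". It makes no exception for AE or lack-of-effect stops. Shell Table 14.0.2 lists a missed Day 85 IGA as a reason for PP exclusion, also without exception.

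**Missing data.** SAP 6.1.5 uses LOCF for ITT and mITT, but "Summary of efficacy variables for the PP subjects will be based on available data". The programming note for PP Table 14.2.1.3 replaces the LOCF footnote with a statement that nothing was imputed.

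**Windows.** Under SAP 6.1.3, early-termination data are mapped to a visit by study day. Days 71 to 98 map to Day 85.

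**The concern.** The inclusion sentence appears meant to stop PP from becoming a completers-only set that loses subjects whose treatment failed or was not tolerated. The rules around it work against that aim. If the exclusions govern, a subject who stops early leaves PP. If the inclusion sentence governs, the subject is counted in the PP N but, without a Day 85 value, is missing from n and from the logistic regression. A programmer cannot tell which reading is intended, and neither reading gives these subjects a Day 85 outcome.

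At stake is the supportive PP estimate of IGA success. When the missing subjects are non-responders, the denominator shrinks, the numerator does not, and the PP rate rises in each arm that has such stops.

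**Working it through.** The plan gives no response rate, dropout rate or effect size, so there is no figure of its own to reproduce.

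**1. Which exits have a Day 85 value?** Inputs: the SAP 6.1.3 windows (Day 15: 9–21; Day 29: 22–42; Day 57: 43–70; Day 85: 71–98) and the 6.4.5 limit of 85 ± 7, that is Days 78–92. An exit visit mapped to Day 85 is treated here as the Day 85 visit.

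| Exit IGA on study day | Mapped to Day 85? | Within ±7 days? | In the PP Day 85 analysis? |
|---|---|---|---|
| 2–70 (69 days) | No | No | No, on either reading |
| 71–77 (7 days) | Yes | No | Only if the inclusion sentence overrides the limit |
| 78–84 (7 days) | Yes | Yes | Yes |

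The days total 69 + 7 + 7 = 83. An exit before Day 22 also has neither a Day 29 nor a Day 57 visit. These are counts of calendar days, not of subjects, because the documents do not say when stops are expected.

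**2. Does the compliance rule also remove them?** SAP 6.11.1 counts expected applications up to the date participation ended. Take first dose and randomisation on Day 1, last evening dose on Day L, exit on Day E and no missed doses. Compliance is then 2L/2E = L/E, which is below 80% only when E > 1.25 × L.
- L = 29, E = 30: 29/30 = 96.7%, compliant.
- L = 29, E = 40: 29/40 = 72.5%, not compliant.
- L = 10, E = 14: 20/28 = 71%, not compliant.

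So it removes only subjects whose exit is well after the last dose.

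**3. Size, under assumed counts.** Suppose PP has 80 subjects per arm with a Day 85 IGA, and 24 active against 12 vehicle successes. With the stops dropped, the difference is 24/80 − 12/80 = 30.0% − 15.0% = 15.0 points. With the stops kept as failures:

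| Stops, active vs vehicle | Calculation | Difference | Shift from dropping them |
|---|---|---|---|
| 10 vs 3 | 24/90 − 12/83 | 12.2 | +2.8 |
| 8 vs 4 | 24/88 − 12/84 | 13.0 | +2.0 |
| 6 vs 6 | 24/86 − 12/86 | 14.0 | +1.0 |
| 4 vs 8 | 24/84 − 12/88 | 14.9 | +0.1 |
| 3 vs 10 | 24/83 − 12/90 | 15.6 | −0.6 |

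For scale, the standard error of the 15.0-point difference is √(0.30 × 0.70/80 + 0.15 × 0.85/80) = 6.5 points.

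**4. Under no effect.** Take 20/100 in each arm with all stops counted as failures, a difference of 0.0. Dropping 15 active and 5 vehicle stops gives 20/85 − 20/95 = 23.5% − 21.1% = +2.5 points. Reversing the stops gives −2.5 points.

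**The case against.** **The inclusion sentence is a specific exception.** It directly follows the exclusion list, and Listing 16.2.3 has a column headed Exceptions, which fits an intended override. On that reading these subjects are in PP. They contribute to the Day 15, 29 and 57 analyses and, as censored observations, to time to IGA success. This is a reasonable reading, but nothing in the SAP states it, 6.1.9 contradicts it, and it does not supply a Day 85 outcome.

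**Late exits do count.** A reader might infer that the sentence has no effect at all on the PP primary endpoint. Windowing shows otherwise: for exits on Days 71–77 it can decide inclusion. The protocol also aims for Day 85 assessments at early discontinuation (Protocol Summary, Section 4.3, Table 4 footnote b). Protocol 6.3.8, however, limits that attempt to reasons other than an AE. These passages need to be reconciled, because they determine whether an AE stop has an exit IGA.

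**AE stops are not all failures.** A subject who leaves for a related AE may have been clear or almost clear at the last IGA. This stands. Scoring such a subject as not achieving success is a choice, and LOCF is an alternative.

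**PP is only supportive.** The primary analysis is ITT with LOCF, the repeated-measures and tipping-point analyses are also on ITT, and all tests are exploratory. This stands and limits the importance of the point.

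**Conclusion.** The point holds. On either reading of SAP 6.4.5, a subject who discontinues before Day 71 for a related AE or lack of effect is absent from the PP Day 85 analysis, although the SAP says such subjects are included.

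The PP success rate rises when the absent subjects are non-responders. The effect on the treatment difference ranges from about +2.8 to −0.6 points across the assumed counts, all within one standard error. A reader might infer that the plan favours the active arm. The documents do not support that: they give no expected stop rates by arm, SAP 6.1.5 expects dropout not to differ between groups, and the sign depends on which arm has more such stops. Nor do they support reading the compliance rule as a general second route to exclusion, since it acts only when exit is later than about 1.25 times the last-dose day.

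The ITT primary analysis does not change. This should be corrected before unblinding, but no primary conclusion depends on it.

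**What to change.** 1. In SAP 6.4.5 and 6.1.9, state that subjects who discontinue for a related AE or documented lack of effect are exempt from the Day 85 completion, missing Day 85 IGA, missed-visit, ±7-day and compliance criteria.
2. In SAP 6.1.5, state that when such a subject has no Day 85 IGA, the subject is scored as not achieving IGA success at Day 85 in the PP responder analyses. Amend the no-imputation footnotes to match in PP Tables 14.2.1.3, 14.2.1.7 and 14.2.2.2.3, and for the Day 85 rows of 14.2.3.6.3. Say explicitly whether the PP continuous endpoints stay on available data.
3. Name the data source for documented lack of effect. Shell Table 14.0.1 has no such discontinuation reason; the nearest is worsening condition.

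The cost is SAP wording and shell footnotes, with no new data collection. PP success rates become slightly lower, and PP handling of these subjects then differs from the LOCF used for ITT and mITT, which the report should say.

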### **6.5 Demographic and Other Baseline Characteristics**

All Baseline summaries will be done on the ITT, mITT, PP, and Safety populations.

Sex, race, and ethnicity will be summarized by counts and percentages. Age, height (cm), and weight (kg) will be summarized with descriptive statistics.

Baseline total BSA affected by AD and duration of AD will be summarized with descriptive statistics. Baseline IGA will be summarized by counts and percentages.

The duration of AD will be calculated as follows:

$$\text{Duration of AD} = \text{year of Baseline visit} - \text{year of AD diagnosis} + 1.$$

Medical histories will be coded using the MedDRA dictionary and presented in a by-subject listing.

## **6.6 Prior and Concomitant Medications**

Concomitant medications will be coded to preferred name and Anatomical Therapeutic Chemical (ATC) classification of ingredients using the WHO-DDE terminology.

Counts and percentages will be provided to summarize the use of concomitant medications other than the study drug reported throughout the study. The number and percent of subjects who took other therapy will be shown by ATC level 2 term and preferred name. Medications which start prior to first application will be considered prior medications. Ongoing medications and medications ending after the date of first application will be considered concomitant medications. Incomplete start and end dates which could be either prior to first application or after first application will be considered prior to first application.

A by-subject listing of all prior and concomitant medications will be presented.

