Number of Subjects Included in the ITT Population	xx ( xx.x%)	xx ( xx.x%)
Number of Subjects Excluded from the ITT Population	xx ( xx.x%)	xx ( xx.x%)
Reason for Exclusion from the ITT Population		
At Least One Post-Baseline Efficacy Assessment	xx ( xx.x%)	xx ( xx.x%)
Number of Subjects Included in the mITT Population	xx ( xx.x%)	xx ( xx.x%)
Number of Subjects Excluded from the mITT Population	xx ( xx.x%)	xx ( xx.x%)
Reason for Exclusion from the mITT Population a		
Not in the ITT Population	xx ( xx.x%)	xx ( xx.x%)
No New Post-Baseline Areas of Atopic Dermatitis b	xx ( xx.x%)	xx ( xx.x%)
Number of Subjects Included in the Safety Population	xx ( xx.x%)	xx ( xx.x%)
Number of Subjects Excluded from the Safety Population	xx ( xx.x%)	xx ( xx.x%)
Reason for Exclusion from the Safety Population a		
No Evidence of Subject Dosing	xx ( xx.x%)	xx ( xx.x%)
No Post Baseline Safety Assessment	xx ( xx.x%)	xx ( xx.x%)

a Table includes primary reason (assigned in order presented in table) subject was excluded.

b The presence of new areas of atopic dermatitis were determined by post-baseline reports compared to baseline reports of BSA.

c See Listing 16.2.3 for a complete list of all other reasons for exclusion from the PP population.

Note: The ITT exclusion of not being randomized is not presented as the table is on randomized subjects.

Percentages are based on the number of randomized subjects.

SOURCE: USERNAME/SPONSOR/PROJECT/JOBNAME (DATE,TIME)

Table 14.0.2: Summary of Subjects Excluded from Analyses  
(Randomized Subjects)  
(Page 2 of 2)

	BTX 1204 4% BID (N=xxx)	Vehicle BID (N=xxx)
Number of Subjects Included in the PP Population	xx ( xx.x%)	xx ( xx.x%)
Number of Subjects Excluded from the PP Population	xx ( xx.x%)	xx ( xx.x%)
Reason for Exclusion from the PP Population a		
Violated the Inclusion/Exclusion Criteria	xx ( xx.x%)	xx ( xx.x%)
Received an Interfering Medication	xx ( xx.x%)	xx ( xx.x%)
Missed Investigator Global Assessment at Day 85	xx ( xx.x%)	xx ( xx.x%)
Missed Both Day 29 and Day 57 Visits	xx ( xx.x%)	xx ( xx.x%)
Not Compliant with Dosing Regimen	xx ( xx.x%)	xx ( xx.x%)
Day 85 Visit not within +/- 7 days Window	xx ( xx.x%)	xx ( xx.x%)
Other c	xx ( xx.x%)	xx ( xx.x%)

a Table includes primary reason (assigned in order presented in table) subject was excluded.

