**Programming note:** *Replace footnote with* - Note: Percentages are based on the number of subjects in the Safety population with a non-missing response.

Table 14.1.2.1: Summary of Baseline Characteristics  
(ITT Population)  
(Page 1 of 2)

	BTX 1204 4% BID (N=xxx)	Vehicle BID (N=xxx)
Height (cm)		
n	XX	XX
Mean	XX.X	XX.X
SD	XX.XX	XX.XX
Median	XX.X	XX.X
Min., Max.	XX, XX	XX, XX
Weight (kg)		
n	XX	XX
Mean	XX.X	XX.X
SD	XX.XX	XX.XX
Median	XX.X	XX.X
Min., Max.	XX, XX	XX, XX
Investigator Global Assessment		
n	XX	XX
0 - Clear	XX ( XX.X%)	XX ( XX.X%)
1 - Almost Clear	XX ( XX.X%)	XX ( XX.X%)
2 - Mild	XX ( XX.X%)	XX ( XX.X%)
3 - Moderate	XX ( XX.X%)	XX ( XX.X%)
4 - Severe	XX ( XX.X%)	XX ( XX.X%)
Total Body Surface Area Affected by AD		
n	XX	XX
Mean	XX.X	XX.X
SD	XX.XX	XX.XX
Median	XX.X	XX.X
Min., Max.	XX, XX	XX, XX

a Duration of AD is calculated as year of Baseline visit – year of AD diagnosis.  
SOURCE: USERNAME\SPONSOR\PROJECT\JOBNAME (DATE,TIME)

Table 14.1.2.1: Summary of Baseline Characteristics  
 (ITT Population)  
 (Page 2 of 2)

	BTX 1204 4% BID (N=xxx)	Vehicle BID (N=xxx)
Duration of AD (Years) a		
n	xx	xx
Mean	xx.x	xx.x
SD	xx.xx	xx.xx
Median	xx.x	xx.x
Min., Max.	xx, xx	xx, xx

a Duration of AD is calculated as year of Baseline visit – year of AD diagnosis + 1.  
 SOURCE: USERNAME\SPONSOR\PROJECT\JOBNAME (DATE,TIME)

Repeat Table 14.1.2.1 for the following:

Table 14.1.2.2: Summary of Baseline Characteristics (mITT Population)

Table 14.1.2.3: Summary of Baseline Characteristics (PP Population)

Table 14.1.2.4: Summary of Baseline Characteristics (Safety Population)

Table 14.1.3.1: Summary of Concomitant Medications by ATC Level 2 Term and Preferred Name  
(ITT Population)  
(Page 1 of x)

ATC Level 2 Term Preferred Name a	BTX 1204 4% BID (N=xxx)	Vehicle BID (N=xxx)
Subjects with at Least One Concomitant Medication Reported	xx ( xx.x%)	xx ( xx.x%)
ATC Level 2 Term 1	xx ( xx.x%)	xx ( xx.x%)
Preferred Name 1	xx ( xx.x%)	xx ( xx.x%)
Preferred Name 2	xx ( xx.x%)	xx ( xx.x%)
...	xx ( xx.x%)	xx ( xx.x%)
Preferred Name x	xx ( xx.x%)	xx ( xx.x%)
...		

a WHO-DDE, Format B2, Version xxxxx.

Note: Concomitant medications are those used on or after the date of first application of study medication.

Percentages are based on the number of subjects in each treatment group in the ITT population.

Subjects are only counted once per ATC Level 2 Term and once per Preferred Name.

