SOURCE: USERNAME\SPONSOR\PROJECT\JOBNAME (DATE,TIME)

Repeat Table 14.1.3.1 for the following:

Table 14.1.3.2: Summary of Concomitant Medications by ATC Level 2 Term and Preferred Name (mITT Population)

**Programming note:** Replace 3rd footnote with - Percentages are based on the number of subjects in each treatment group in the mITT population.

Table 14.1.3.3: Summary of Concomitant Medications by ATC Level 2 Term and Preferred Name (PP Population)

**Programming note:** Replace 3rd footnote with - Percentages are based on the number of subjects in each treatment group in the PP population.

Table 14.1.3.4: Summary of Concomitant Medications by ATC Level 2 Term and Preferred Name (Safety Population)

**Programming note:** Replace 3rd footnote with - Percentages are based on the number of subjects in each treatment group in the Safety population.

Table 14.1.4.1: Summary of Concomitant Antibiotic Therapies by ATC Level 2 Term and Preferred Name  
(ITT Population)  
(Page 1 of x)

ATC Level 2 Term Preferred Name a	BTX 1204 4% BID (N=xxx)	Vehicle BID (N=xxx)
Subjects with at Least One Concomitant Antibiotic Therapy Reported	xx ( xx.x%)	xx ( xx.x%)
ATC Level 2 Term 1	xx ( xx.x%)	xx ( xx.x%)
Preferred Name 1	xx ( xx.x%)	xx ( xx.x%)
Preferred Name 2	xx ( xx.x%)	xx ( xx.x%)
...	xx ( xx.x%)	xx ( xx.x%)
Preferred Name x	xx ( xx.x%)	xx ( xx.x%)
...		

a WHO-DDE, Format B2, Version xxxxx.

Note: Concomitant antibiotic therapies are those used on or after the date of first application of study medication.

Percentages are based on the number of subjects in each treatment group in the ITT population.

Subjects are only counted once per ATC Level 2 Term and once per Preferred Name.

SOURCE: USERNAME\SPONSOR\PROJECT\JOBNAME (DATE,TIME)

Repeat Table 14.1.4.1 for the following:

Table 14.1.4.2: Summary of Concomitant Antibiotic Therapies by ATC Level 2 Term and Preferred Name (mITT Population)

**Programming note:** Replace 3rd footnote with - Percentages are based on the number of subjects in each treatment group in the mITT population.

Table 14.1.4.3: Summary of Concomitant Antibiotic Therapies by ATC Level 2 Term and Preferred Name (PP Population)

**Programming note:** Replace 3rd footnote with - Percentages are based on the number of subjects in each treatment group in the PP population.

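### SAP 6.6 treats an ambiguous incomplete medication end date as before first application, so a drug possibly used on study can leave the concomitant tables; SAP 6.1.5 and the table footnotes say otherwise

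*SAP*

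**What the plan says.** SAP 6.6 defines the two classes separately. For prior use: "Medications which start prior to first application will be considered prior medications". For concomitant use: "Ongoing medications and medications ending after the date of first application will be considered concomitant medications". A drug may be both. The section then settles doubtful dates in one direction: "Incomplete start and end dates which could be either prior to first application or after first application will be considered prior to first application". The sentence names end dates as well as start dates.

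Two other places bear on the same record:

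- SAP 6.1.5 gives a general rule for partial dates. A missing day is set to day 1, with one exception: "unless the month is the same month as the first application of study drug then the day will be that of first application". A missing month is handled in the same way by year. The rule is not limited to start dates.
- The footnote to Table 14.1.3.1 reads: "Concomitant medications are those used on or after the date of first application of study medication". The antibiotic tables carry a matching note: "Concomitant antibiotic therapies are those used on or after the date of first application of study medication". SAP 6.7, which introduces those tables, has no date rule of its own.

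SAP 6.4.5 removes subjects from the PP set who "Have taken any interfering concomitant medication". Table 14.0.2 labels that reason "Received an Interfering Medication".

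**The concern.** The concomitant medication tables show, by arm, what else subjects used while efficacy was being measured. Protocol 6.5 prohibits other AD treatments and antibiotics. Protocol 6.6 allows that additional treatment may be given, with continuation decided case by case. Such drugs can affect the efficacy result, so a reader will look for them in these tables.

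A rule that assumes an incompletely dated drug stopped before dosing omits it silently. The table gives no sign that a doubtful record was left out. Antibiotics deserve particular attention. Protocol 4.2 has no antibiotic-specific washout, and Protocol 6.5 has antibiotic use noted as a deviation, but SAP 6.3 says that deviations are not entered in the database. The medication record and its classification therefore carry more weight.

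Because SAP 6.1.5, SAP 6.6 and the footnotes differ, two programmers following the SAP could also produce different counts from the same data.

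**Working it through.** The plan states no figure on this point. The check is to apply the rules to every possible date pattern.

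**Step 1. Which patterns are lost.** Start can be before first application, after it, or ambiguous. End can be before, after, ongoing, or ambiguous. That gives 3 × 4 = 12 patterns, less one impossible one (start after, end before) = 11. SAP 6.6 is applied with ambiguous set to before.

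| Start | End | On-study use possible | Concomitant under 6.6 |
|---|---|---|---|
| before | before | no | no |
| before | after | yes | yes |
| before | ongoing | yes | yes |
| before | ambiguous | yes | **no** |
| after | after | yes | yes |
| after | ongoing | yes | yes |
| after | ambiguous | yes | **no**, only if each date is judged alone |
| ambiguous | before | no | no |
| ambiguous | after | yes | yes |
| ambiguous | ongoing | yes | yes |
| ambiguous | ambiguous | yes | **no** |

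Nine patterns allow on-study use. Three of the nine are lost on the most literal reading, all through the end date. If the start is known to be after first application, the end cannot fall on either side of it, so on a natural reading the sentence does not apply and two patterns are lost. An ambiguous start with a known later end, or with ongoing use, stays concomitant.

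**Step 2. The rules side by side.** Take first application on 15 June, an earlier start, and an end date of June with the day missing.

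- SAP 6.6, ambiguity sentence: the end is before 15 June, so the drug is prior only.
- SAP 6.1.5, then the 6.6 definition: the end is 15 June, which is not after 15 June, so the drug is not concomitant.
- SAP 6.1.5, then the table footnote: the end is 15 June, which is on or after 15 June, so the drug is concomitant.

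**Step 3. SAP 6.1.5 applied to an end date in a later month.** Take dosing begun in June, a drug started on 10 July, and an end date of July with the day missing. The rule gives 1 July, nine days before the start.

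**Step 4. How much on-study time an ambiguous end date can cover.** The first-application dates and end-day distributions here are assumptions.

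- Day missing, 30-day month, first application on day d. Days left after it are 30 − d. The mean share over d = 1 to 30 is (29 + 28 + … + 0) / (30 × 30) = 435/900 = 48.3%. By symmetry 48.3% of days fall before first application, and 30/900 = 3.3% fall on it.
- Day missing, all dates of a 365-day year. Days left sum to 465 in a 31-day month, 435 in a 30-day month and 378 in February. The mean is (7 × 465 + 4 × 435 + 378) / 365 = 5373/365 = 14.7 days, with a range of 0 to 30.
- Month missing. Treatment runs 84 days, so 83 follow Day 1. Between 0 and 83 can be covered. All 83 are covered when at least 83 days of the year remain: 364 − 83 + 1 = 282 first-application dates, and 282/365 = 77%.

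These figures describe how wide the doubt is for one record. They do not estimate how many records are misclassed.

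**The case against.** The strongest reply is that the gap is narrow and has little consequence. Most of that stands.

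- **Scope.** The loss needs an incomplete end date in the month or year of first application, together with a start that is earlier or also incomplete. New drugs with a known on-study start, ongoing drugs, and drugs with a known later end are safe. A reader might infer that every ambiguous date hides a drug; the table above shows that this is not so.
- **PP set.** A reader might also infer that subjects who used an interfering drug on study will stay in PP. The SAP does not tie that exclusion to the 6.6 flag. Table 14.0.2 omits the word concomitant, the by-subject listing shows every drug, and SAP 6.1.9 settles violations in a blinded evaluability review. The eligibility criterion is a further check. Protocol 4.2 requires 14 days free of topical corticosteroids before Baseline. If dosing began on days 1 to 14 of a month, a topical steroid placed earlier in that month is itself a washout breach.
- **Antibiotics.** SAP 6.7 has the sponsor determine these before lock, and their footnote says on or after. They are lost only if the 6.6 date rule is carried over to those tables, which the SAP neither says nor excludes.
- **Conflict with 6.1.5.** SAP 6.6 is the rule specific to medications and may be meant to override. SAP 6.1.5 names only AE start dates as an application of its rule. But its wording covers any partial date and no precedence is stated. Even if 6.6 governs, its text still differs from the footnotes.
- **Data quality.** Medications are queried at each visit, and Protocol 8 and 10 provide full source verification and queries on missing data. Incomplete dates may be few.
- **Direction of error.** Under the uniform assumption, resolving doubt the other way also misclasses 48.3% of these records. That is a real cost. The difference is that the overcount shows in the table, while the omission does not.

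**Conclusion.** The point holds for incomplete end dates. SAP 6.6 contains an explicit rule under which a drug possibly used on study is counted as prior only and leaves the concomitant medication tables. That rule conflicts with SAP 6.1.5 and with the table footnotes. It affects two of the nine patterns that allow on-study use, or three if each date is judged alone.

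The size in practice is unknown, because the documents do not say how many incomplete dates to expect. The 48% is not a misclassification rate. It rests on a uniform end day and a uniform day of first application, and required washouts make earlier end dates more likely for some drugs.

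The documents do not support a claim that the PP set will be biased; that effect is only possible. The primary ITT analysis does not use the classification. This is a correction worth making before lock, not a threat to the main result.

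**What to change.** 1. In SAP 6.6, replace the sentence on incomplete dates. A medication is concomitant unless the known parts of its end date show that it ended before first application.
2. Use *on or after* first application in the 6.6 definition so that it matches the footnotes to the medication and antibiotic tables, and state that the same date rule applies in SAP 6.7.
3. Limit the SAP 6.1.5 imputation to start dates. Impute a partial end date to the last possible day, capped at study exit. This also removes ends that precede starts.
4. Decide PP exclusion for an interfering drug with an ambiguous end date in the blinded evaluability review, not from the imputed flag alone.

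With change 1, all nine patterns that allow on-study use are classed as concomitant.

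The cost is a few sentences in the SAP and one programming rule, with no new data. The downside is that some truly prior medications will be counted as concomitant. Change 4 keeps that overcount from removing properly washed-out subjects from PP automatically.
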